6.1.4 Demographics and Baseline Characteristics

Demographic data will be summarized using descriptive summary statistics by cohort and overall in the safety population. A by-subject listing will be provided for demographic data.

6.1.4.1 Demographics

The demographic characteristics include

- Age (continuous), age is calculated based on year of informed consent and year of birth per EDC system.
- Sex (Male, Female) and Childbearing Potential Status for Female
- Race
- Ethnicity
- Baseline Height (in cm)
- Baseline Weight (in kg)
- Baseline Body Mass Index (BMI; in kg/m²)

6.1.4.2 Disease-Specific Baseline Disease Characteristics

Disease-specific baseline characteristics include:

- Number of Anti-Cancer Regimens
- Time Since Completion of Last Regimen in Months

- Best Response of Last Regimen
- Time Since Initial Diagnosis of Cancer in Months
- ECOG Performance Status
- Stage at Diagnosis
- Stage at Study Entry
- Primary Site of Cancer
- Specific Histology

6.1.5 Medical History

Medical history will be coded using MedDRA 21.1 or later, sorted alphabetically by system organ class and preferred term, summarized for the safety population. By-subject listings will be provided for medical history.

6.1.6 Prior and Concomitant Medications

The World Health Organization Drug Dictionary (WHODrug-Global-B3) will be used to classify concomitant medications by therapeutic class and generic name.

Prior and concomitant medications, defined below, are summarized by Preferred Term (PT) for Safety Population.

- Medication started prior to first dose of any study drug will be considered as prior medication.
- Concomitant medication is defined as all medications used on or after the first dose of any study drug, through the treatment phase and for 30 days following the last dose of any study drug. A medication can be classified as both prior and concomitant medication.

Subjects reporting more than one use of the same medication will be counted only once in the summary tables. All medications will be sorted by descending total frequency of PT.

All prior and concomitant medications will be provided in a by-subject listing for Safety Population.

6.1.7 Prior Anticancer Therapy

Number of prior regimens, time since the completion of last regimen will be summarized by treatment group using descriptive statistics. The best response to the last regimen will be summarized using summary statistics for a categorical variable. The summaries will be based on the Safety population as part of the disease-specific baseline characteristics.

The anti-cancer treatment, anti-cancer radiotherapy, anti-cancer surgery and procedures will be provided separately in a by-subject listing for Safety Population.

6.2 Efficacy Analyses

Tumor response assessment will be performed by the investigator per RECIST v1.1 guidelines. The tumor response will be classified to: complete response [CR], partial response [PR], stable disease [SD], or progressive disease [PD].

The Efficacy analyses listed in the [Table 9](#) will be performed on the efficacy population as primary analysis, and on the response-evaluable population as a sensitivity analysis. Efficacy analysis will be performed separately for Phase 1a Monotherapy Dose Escalation/Exploration, Phase 1b Monotherapy Dose Expansion and Phase 1a Combination Dose Escalation/Exploration.

Table 9 Efficacy analysis

Phase	Efficacy Endpoint	Efficacy Analysis
Phase 1a Monotherapy Dose Escalation/Exploration	Exploratory	[REDACTED]
Phase 1b Monotherapy Dose Expansion	Secondary	ORR, DOR, PFS, DCR
	Exploratory	[REDACTED]
Phase 1a Combination Dose Escalation/Exploration	Secondary	ORR
	Exploratory	[REDACTED]

6.2.1 Efficacy Endpoint: ORR

Objective Response Rate (ORR) is defined as the total number of patients with confirmed responses of either complete response (CR) or partial response (PR), as determined by the investigator per RECIST v1.1, divided by the total number of patients who are evaluable for a response. The best overall response (BOR) is the best response documented from first dose until the end of study, first disease progression, death, or start of new anti-cancer therapy, whichever is earlier. Subjects, who do not have sufficient baseline or on-study tumor status information to be adequately assessed for response status (i.e., those with BOR of not evaluable [NE]), or received anticancer therapy other than the study treatment, will be considered as non-responders and will be included in the denominators in calculations of response rates.

For the confirmed BOR, the algorithm below should be followed. The hierarchy of the categories for confirmed BOR is in the order listed.

- Confirmed CR: Check if the longest consecutive duration of CR (allow NE in between; duration starts at CR and ends at CR) is ≥ 4 weeks, if yes, set BOR to CR; otherwise:
- Confirmed PR: Check if the longest consecutive duration of PR (allow NE or CR in between; duration starts at PR and ends at PR/CR) is ≥ 4 weeks, if yes, set BOR to PR; otherwise:
- SD: Check if the best time-point response is CR or PR or SD, if yes, set BOR to SD; otherwise:

- PD: Check if the best time-point response is PD, set confirmed BOR to PD.
- NE: Otherwise set to NE.

Estimate of ORR and corresponding 2-sided exact 90% CI using the Clopper-Pearson method will be provided by treatment and overall. The Clopper-Pearson exact 90% CIs will be from SAS FREQ procedures with option BINOMIAL (EXACT). Patients who don't have any postbaseline adequate tumor assessments will be counted as non-responders.

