### 6.8.1 Permitted Concomitant Medications

Supportive care (e.g., antiemetics, analgesics, bisphosphonates, and RANK-L inhibitors) may be used at the investigator's discretion and in accordance with institutional procedures. Patients should receive antiemetic and other prophylactic treatments according to the local standard of care and manufacturer's instruction. Patients should receive full supportive care, transfusions of blood and blood products, antibiotics, antiemetics, etc., when appropriate. Hematopoietic stimulating agents may be used if indicated. Short course of focal radiation for palliation of symptoms is allowed. Patients are permitted to use topical, ocular, intra-articular, intranasal, and inhaled corticosteroids (with minimal systemic absorption). Adrenal replacement steroid doses > 10 mg daily prednisone are permitted. A brief (approximately less than 3 weeks) course of corticosteroids for prophylaxis (e.g., contrast dye allergy) or for treatment of non-autoimmune conditions (e.g., delayed-type hypersensitivity reaction caused by a contact allergen) and for the treatment of tumor-related AEs is permitted.

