### 6.8.2 Prohibited Concomitant Medications

Concomitant anticancer therapies of any kind including extensive non-palliative radiation are not permitted. Immunosuppressive doses of systemic corticosteroids are prohibited (unless utilized to treat a drug-related AE).

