2.2.3 FPT155 Monotherapy Dose Expansion

Enrollment in Phase 1b dose expansion will begin when the MTD and/or RD has been identified by the Cohort Review Committee (CRC). Up to 8 tumor-specific cohorts consisting of approximately 30 patients each will evaluate the safety, efficacy, PK, and PD of FPT155 at the RD. Patients with advanced renal cell carcinoma (RCC) and melanoma that have failed prior anti-programmed death-ligand 1 (anti-PD[L]1) therapy will be enrolled in 2 of the 8 cohorts. Additional tumor types are specified in [Table 3](#) for the remaining Phase 1b cohorts and will be determined based on emerging safety, translational, and clinical data for FPT155, as well as any potential new safety signals from other immunotherapies, such as significant changes to prescribing information for approved immunotherapies.

Table 3 Additional Cohorts for Phase 1b Expansion

Phase 1b Cohort	Inclusion Criteria
1	Patients with advanced renal cell carcinoma as specified per Section 5.2 of the protocol.
2	Patients with advanced melanoma as specified per Section 5.2 of the protocol.
3	Patients with previously-treated unresectable or metastatic solid tumors with deficient mismatch repair (dMMR) or high microsatellite instability (MSI-H) and an absence of suitable standard treatment options.
4	Patients with previously-treated unresectable or metastatic non-small cell lung cancer and an absence of suitable standard treatment options.
5	Patients with previously-treated solid tumors with a response to prior PD-1 or PDL-1 directed treatment as defined by an objective response (partial or complete response) or a minimum of three months on prior PD-1 or PDL-1 directed therapy.

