6.2.2 Efficacy Endpoint: DCR

Disease Control Rate (DCR) is defined as total number of patients with confirmed responses of either CR, PR, or stable disease as determined by the investigator per RECIST v1.1, divided by the total number of patients who are evaluable for a response.

Estimate of DCR and corresponding 2-sided exact 90% CI using the Clopper-Pearson method will be provided by treatment and overall. The Clopper-Pearson exact 90% CIs will be from SAS FREQ procedures with option BINOMIAL (EXACT).

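### SAP 6.2.1 makes anyone who received other anticancer therapy a non-responder with no timing limit, so a confirmed response could be erased by later treatment

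*SAP*

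**What the plan says.** SAP 6.2.1 deals with other anticancer therapy twice, in adjacent sentences.

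- The BOR sentence counts the best response from first dose to the earliest of end of study, "first disease progression, death, or start of new anti-cancer therapy, whichever is earlier".
- The next sentence covers subjects whose tumor data are insufficient, and then adds those who "or received anticancer therapy other than the study treatment, will be considered as non-responders and will be included in the denominators". Nothing says when that therapy must have been received.

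The section then prescribes a step-by-step derivation: "For the confirmed BOR, the algorithm below should be followed". Its steps run through confirmed CR, confirmed PR, SD, PD and NE. None mentions other therapy.

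Two other places bear on the rule. Protocol Table 11 defines ORR as the share of patients with a confirmed BOR of CR or PR, with no therapy exclusion. SAP Table 10 has a row that censors duration of response (DOR) at the last evaluable scan before subsequent therapy.

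On populations, SAP 6.2 says that the efficacy analyses "will be performed on the efficacy population as primary analysis, and on the response-evaluable population as a sensitivity analysis". SAP Table 9 lists ORR and the disease control rate (DCR) as secondary for Phase 1b, and ORR as secondary for the combination part.

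**The concern.** The two sentences give different answers for the same patient. Under the BOR window, a response confirmed before new therapy stands. Under the next sentence, receipt of other therapy at any time removes it.

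The data that would trigger the rule will be in the database. New anticancer therapy must be documented during long-term follow-up (SAP Appendix 2), and subsequent treatment is listed by subject (SAP 6.2.5). A programmer could therefore implement the rule as any other therapy after first dose. The result would look plausible and raise no alarm. The error runs in one direction only, because reclassification can remove responders but never add them.

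**Working it through.** **Step 1. Apply each text to one patient.** Take a Phase 1b patient on the planned scan schedule (every 6 weeks for 24 weeks), with PR at week 6, PR at week 12, progression at week 24, and another therapy afterwards.

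- BOR window: it closes at week 24, and both PRs fall inside it.
- Algorithm: PR lasts from week 6 to week 12, which is 6 weeks and meets the 4-week minimum. BOR is confirmed PR.
- Protocol Table 11: responder.
- SAP 6.2.3: the patient contributes a DOR from week 6 to week 24.
- Therapy clause as written: non-responder.

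The patient would have a DOR but be missing from the ORR numerator.

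**Step 2. Move the new therapy earlier.**

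- Started after the week 12 scan, without progression: the PR is already confirmed inside the window. The subsequent-therapy row of Table 10 censors DOR at week 12, which presumes that the patient is a responder. The clause says non-responder.
- Started between weeks 6 and 12: the window closes before confirmation, so the algorithm gives SD. The patient is a non-responder without the clause.

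The clause therefore changes the answer only for responses already confirmed. Where it would be sensible, the window has done the work.

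**Step 3. Reproduce the SAP's precision table.** Inputs: n = 25 and a two-sided exact 90% interval (SAP 2.3, Table 4; SAP 6.2.1). With x responders, the Clopper-Pearson limits are

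- lower = 5th percentile of Beta(x, n − x + 1)
- upper = 95th percentile of Beta(x + 1, n − x)

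For x = 6 these are the 5th percentile of Beta(6, 20) = 11.0% and the 95th percentile of Beta(7, 19) = 42.0%. The table prints 11% and 42%. The other five rows also agree after rounding: 5/25, 8.2–37.5; 7/25, 14.0–46.2; 8/25, 17.0–50.4; 9/25, 20.2–54.4; 10/25, 23.6–58.3. Wilson (13.0–40.1 at 6/25) and Agresti-Coull (12.7–40.3) do not match. The table is correct and uses the method named in 6.2.1.

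**Step 4. Size of the effect.** SAP 2.3 chose n = 25 so that 10% is excluded when the observed ORR is 24% or higher, that is, from 6/25. The number of confirmed responders who later receive other therapy is assumed.

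| Responders reclassified | ORR | 90% CI | Excludes 10%? |
|---|---|---|---|
| 0 | 6/25 = 24% | 11.0–42.0% | yes |
| 1 | 5/25 = 20% | 8.2–37.5% | no |
| 2 | 4/25 = 16% | 5.7–33.0% | no |
| 3 | 3/25 = 12% | 3.4–28.2% | no |

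The primary analysis uses all treated patients, up to 30 per cohort. There, 7/30 = 23.3% (11.5–39.4%) becomes 6/30 = 20.0% (9.1–35.7%) with one reclassified and 5/30 = 16.7% (6.8–31.9%) with two. Each reclassified patient costs 1/25 = 4.0 points or 1/30 = 3.3 points.

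**The case against.** The best defense is that context supplies the missing timing. The only timing in the paragraph is the BOR window, the algorithm and protocol Table 11 agree with it, and the SAP is meant to detail the protocol's analyses. A sensible analyst would read the clause as therapy before response. That is probably what was meant, and it keeps the point minor. It does not remove the point. The sentence is an explicit rule without that limit, and the reading that does harm can be programmed. Table 10 supports the defense's view of the intent but does not prove it, because its rows also serve PFS.

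Four stronger readings are tempting and are not supported.

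- **ORR would be zero.** Read with no limit at all, the clause also catches prior therapy, which Phase 1b patients must have had; cohort 4, for example, takes "Patients with previously-treated unresectable or metastatic non-small cell lung cancer". That gives 0/30 = 0% (0–9.5%). The reading is absurd and would be noticed at once.
- **DCR has the wrong denominator.** SAP 6.2.2 does say "divided by the total number of patients who are evaluable for a response", and has no sentence of its own about NE patients. But SAP 6.2 already assigns DCR to the efficacy population as primary and the response-evaluable population as sensitivity. With an assumed 15 controlled patients, 15/30 = 50.0% (33.9–66.1%) and 15/25 = 60.0% (41.7–76.4%) would both be reported. Only the phrase is out of line, as it is in the ORR definition.
- **Palliative radiation would trigger the rule.** Protocol 6.8.2 states: "Concomitant anticancer therapies of any kind including extensive non-palliative radiation are not permitted". Protocol 6.8.1 states: "Short course of focal radiation for palliation of symptoms is allowed". Read together, the protocol does not treat the permitted radiation as anticancer therapy.
- **The sample size is wrong.** Step 3 shows that it is not.

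**Conclusion.** The point holds for the therapy clause in SAP 6.2.1, which is wrong as written. It conflicts with the BOR window, the confirmed-BOR algorithm and protocol Table 11, and it sits badly with the DOR censoring row. Applied to therapy after first dose, it biases ORR downward. At the SAP's benchmark of 6/25, a single reclassified responder is enough to lose the exclusion of 10%.

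Severity is minor. The documents give no rate of later therapy, so the counts above are illustrations and no probability attaches to them. ORR is a secondary endpoint, the primary endpoints are safety, and the trial is for estimation, with no hypothesis. The exclusion of 10% is a planning aim for precision and not a decision rule.

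**What to change.** In SAP 6.2.1, do one of the following.

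- Delete the therapy clause and keep the rule for subjects with inadequate tumor data. The BOR window already handles new therapy, provided that it is applied before the confirmation algorithm.
- Or limit the clause to subjects who *started other anticancer therapy after first dose and before a CR or PR was confirmed*.

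In either case, add one sentence saying that therapy started after a confirmed response does not change BOR.

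A wording tidy can go in at the same time. In SAP 6.2.1 and 6.2.2, give the denominator as patients in the analysis population (efficacy primary, response-evaluable sensitivity), and say that NE patients stay in the primary DCR denominator. Align the matching phrase in the protocol at its next amendment.

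The cost is a few SAP sentences, with no new data, visits or patients. No amendment is needed now, because protocol 9.0 requires one only when a principal feature changes, and the primary population stays as it is.

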##### 4.4.3. Best overall response: all time points

The best overall response is determined once all the data for the patient is known.

**Best response determination in trials where confirmation of complete or partial response IS NOT required:** Best response in these trials is defined as the best response across all time points (for example, a patient who has SD at first assessment, PR at second assessment, and PD on last assessment has a best overall response of PR). When SD is believed to be best response, it must also meet the protocol specified minimum time from baseline. If the minimum time is not met when SD is otherwise the best time point response, the patient's best response depends on the subsequent assessments. For example, a patient who has SD at first assessment, PD at second and does not meet minimum duration for SD, will have a best response of PD. The same patient lost to follow-up after the first SD assessment would be considered inevaluable.

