#### 4.6. Confirmatory measurement/duration of response

##### 4.6.1. Confirmation

In non-randomised trials where response is the primary endpoint, confirmation of PR and CR is required to ensure responses identified are not the result of measurement error. This will also permit appropriate interpretation of results in the context of historical data where response has traditionally required confirmation in such trials (see the paper by Bogaerts et al. in this Special Issue). However, in all other circum-

stances, i.e. in randomised trials (phase II or III) or studies where stable disease or progression are the primary endpoints, confirmation of response is not required since it will not add value to the interpretation of trial results. However, elimination of the requirement for response confirmation may increase the importance of central review to protect against bias, in particular in studies which are not blinded.

In the case of SD, measurements must have met the SD criteria at least once after study entry at a minimum interval (in general not less than 6–8 weeks) that is defined in the study protocol.

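### The SAP's confirmed-BOR algorithm sets no minimum time for stable disease, so an SD reading seen only on an early scan counts toward the disease control rate

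*SAP*

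**What the plan says.** SAP section 6.2.1 derives confirmed BOR through a hierarchy. The CR step carries a time condition: "Check if the longest consecutive duration of CR (allow NE in between; duration starts at CR and ends at CR) is ≥ 4 weeks". The PR step has the same 4-week condition. The next step has none: "SD: Check if the best time-point response is CR or PR or SD, if yes, set BOR to SD". The period over which BOR is read starts at first dose, with no lower limit on when a scan counts.

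SAP section 6.2.2 defines DCR as the "total number of patients with confirmed responses of either CR, PR, or stable disease" over patients evaluable for response, by investigator assessment under RECIST v1.1. It adds no duration for SD. On the interval it says: "Estimate of DCR and corresponding 2-sided exact 90% CI using the Clopper-Pearson method will be provided by treatment and overall". SAP Table 9 lists DCR among the Phase 1b secondary endpoints: "ORR, DOR, PFS, DCR".

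The RECIST 1.1 guideline in protocol Appendix 6 says otherwise about SD. Its section 4.4.3 states: "When SD is believed to be best response, it must also meet the protocol specified minimum time from baseline". Its section 4.6.1 states that "measurements must have met the SD criteria at least once after study entry at a minimum interval", normally at least 6 to 8 weeks, to be set by the study protocol. Its Table 3 classes an unconfirmed response followed by PD as SD only if that minimum is met, and as PD otherwise. Followed by NE, the fallback is NE.

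**The concern.** The plan labels DCR as RECIST v1.1 but omits a condition that the appended RECIST text places on SD. Citing RECIST does not repair this, because RECIST leaves the number to the protocol and the protocol gives none. The SD step in SAP 6.2.1 is the only rule in either document that classes a patient as SD, so it governs DCR in practice even though SAP 6.2.2 does not refer to it.

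Adding a minimum can only remove SD classifications, so the error, where it occurs, runs upward. The SD line may carry most of the endpoint. Protocol section 2.3 reports that best response so far has been stable disease apart from one unconfirmed partial response. If Phase 1b looks similar (an assumption), DCR will consist largely of SD, and the same line will decide how unconfirmed PRs are classed.

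**Working it through.** **1. The plan's own figure.** The only precision statement is SAP Table 4 (protocol Table 10), and it concerns ORR. The exact 90% limits are: lower = 5th percentile of Beta(x, n−x+1), upper = 95th percentile of Beta(x+1, n−x). For x = 6, n = 25 this gives 11.0% to 42.0%, matching the stated (11%, 42%). All six rows reproduce. Patients reach the SD step only after failing the CR and PR steps, so ORR and this table do not depend on it. No DCR figure is stated anywhere.

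**2. When can an SD reading first arise?**
- *Scheduled scan:* 6 ± 1 weeks from first dose (protocol Table 2, SAP Appendix 2), so days 35 to 49. None falls before day 35.
- *EOT scan after one dose:* the visit is 28 ± 7 days after the last dose, here 21 to 35 days after first dose. Protocol Table 2 and section 8.1.1 waive the scan if one was done in the previous 8 weeks (56 days). Screening imaging may be up to 28 days before treatment. Taking the screening scan as one that counts, let b be its days before dosing (at most 28) and e the visit day (at most 35). A scan is required only if b + e > 56. That needs e ≥ 29 and b ≥ 22, so a visit at least one day late and a screening scan at least 22 days old at dosing. At the nominal visit, 28 + 28 = 56, and no scan is required. Scans triggered this way fall on days 29 to 35, and only days 29 to 34 are below 35.
- *EOT scan after two doses:* second dose at 21 ± 3 days, plus 28 ± 7, gives 39 to 59 days. All are past day 35.
- *Unscheduled scan:* the schedule headers allow additional tests at any time when clinically indicated, and SAP 6.2.1 does not exclude such scans from BOR. This is the main route, and the documents give no frequency for it.

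**3. What each route does to BOR.** With a reading before day 35 and none of SD or better later:

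| Sequence | SAP 6.2.1 | Appended RECIST text, minimum not met |
|---|---|---|
| early SD, then PD | SD | PD |
| early SD, then no further assessment | SD | NE |
| early unconfirmed PR, then PD | SD | PD |
| early unconfirmed PR, then NE | SD | NE |

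**4. Size per patient.** In the primary efficacy population (all treated, about 30 per cohort), 1/30 = 3.3 points. In the response-evaluable sensitivity set (planned 25), 1/25 = 4.0 points. To illustrate with assumed counts and exact 90% intervals, removing one patient moves 15/30 = 50.0% (33.9 to 66.1) to 14/30 = 46.7% (30.8 to 63.0), or 15/25 = 60.0% (41.7 to 76.4) to 14/25 = 56.0% (37.9 to 73.0).

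**5. Sensitivity to the minimum chosen.** A simulation assumed exponential PFS with medians of 1.5, 2, 3 and 4 months, a first scan uniform over weeks 5 to 7 and a second over weeks 11 to 13, and no unscheduled or EOT scans.

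| Minimum SD time | DCR at median 1.5 / 2 / 3 / 4 months |
|---|---|
| none, or 5 weeks | 52.9% / 62.0% / 72.7% / 78.7% |
| 6 weeks | 39.0% / 49.0% / 61.9% / 69.6% |
| 7 or 8 weeks | 28.0% / 38.4% / 52.9% / 62.0% |

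A 35-day minimum changes nothing for patients scanned on schedule. A 6-week minimum lowers DCR by 9 to 14 points, and 7 or 8 weeks by 17 to 25.

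**The case against.** The strongest reply is that almost nobody is affected. Scheduled scans start at day 35, the 8-week exemption nearly empties the EOT route, and unscheduled early scans have no stated frequency. Such a scan also matters only if no later one, before progression, reads SD or better. DCR is descriptive in a study that declares no hypothesis, it has no decision threshold, and the by-subject tumour response listings would show early-only SD. All of this stands and limits the size of the point. It does not supply the missing condition.

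Three stronger readings are tempting and not supported.
- A reader might infer that patients stopping after one dose are routinely scanned around weeks 4 to 5. The exemption confines this to a late visit combined with an old screening scan.
- A reader might take the 9 to 25 point differences in the simulation as the bias in the plan. They come from minimums of 6 weeks or more, which neither document specifies. They show how much the choice matters, not how far the current rule errs against a 35-day rule.
- A reader might conclude that classing an unconfirmed PR followed by PD as SD is wrong in itself. RECIST Table 3 gives the same result once the minimum is met, so with a 35-day minimum no patient scanned on schedule changes.

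It is also fair to say that 35 days is shorter than the 6 to 8 weeks the appended text describes as usual. That is why a longer, justified minimum should remain open to the sponsor.

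**Conclusion.** The omission is real. SAP 6.2.1 assigns SD regardless of timing, the RECIST text the plan adopts requires a protocol-specified minimum, and none is given. Any error in DCR is upward, by 3.3 points per affected patient with about 30 treated, or 4 points with 25 response-evaluable. The number of affected patients cannot be derived from the documents and is probably small. They would come mainly from clinically indicated early scans, and rarely from an EOT scan on days 29 to 34 after a single dose.

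This rests on DCR using the section 6.2.1 BOR, on a 35-day minimum, and on the screening scan counting toward the 8-week exemption. The documents do not support a claim that DCR is materially inflated, nor any stated number of affected patients. ORR, DOR, PFS and the sample size are unaffected. It is a specification gap in a secondary descriptive endpoint, worth closing before database lock because it is cheap and because the minimum should not be chosen after the data are seen.

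**What to change.** In SAP 6.2.1, change the SD step to require a time-point response of CR, PR or SD at an assessment at least 35 days after first dose (the 6-week scan less its 1-week window). The sponsor may prespecify a longer minimum, with a justification set against the 6 to 8 weeks in the appended RECIST text.

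If the condition is not met, assign PD when the next assessment is PD, and NE otherwise. Write this into the SD step itself. The existing PD step tests whether the best time-point response is PD, so a patient with an early SD followed by PD would fall through it to NE.

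In SAP 6.2.2, state that DCR uses this BOR. That also settles what *confirmed* means for stable disease, which is currently undefined.

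The cost is a short SAP edit and one programming condition, with no new data, visits or patients. The reported DCR may be slightly lower.
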